### D. Treatment Randomization

No randomization will be performed in this study.

### E. Assessment Schedule

See Protocol Table 1 for the study schedule of assessments.

### F. End of Study

Per Sponsor's decision, site activation and study enrollment were terminated officially on 24Jun2022. All subjects previously enrolled in the study may continue receiving up to 2 years of study treatment per the current protocol.

The end of study is defined as the date of the last dose of study treatment for the last ongoing subject, plus 100 days of safety follow-up.

Regeneron Pharmaceuticals Inc. / Protocol: CMP-001-010 IOVIA Biotech (Confidential) Project # RZA44091

### III. Interventions

### A. Clinical Trial Material

Nivolumab is an FDA approved drug product for the treatment of several types of cancer in multiple regions including the US (Dec-2014), the EU (Jun-2015), and Japan (Jul-2014). The physical characteristics of Nivolumab are found in the OPDIVO® (Nivolumab) Prescribing Information. Nivolumab will be provided by the sponsor.

CMP-001 is an investigational study drug and will be provided by the Sponsor. CMP-001 is provided as a 5 mg/mL solution in a single-use vial. The physical characteristics and other details about the CMP-001 study drug are found in the IB and the Pharmacy Manual.

At the end of the treatment period, study treatment will no longer be provided to subjects/investigators unless the Sponsor chooses to extend the study. The investigator should ensure that the subject receives appropriate standard of care to treat the condition under study.

The protocol provides additional product details in Section 6.

## IV. Protocol Objectives

Per Sponsor's decision, enrollment was stopped before reaching the sample size planned for the analyses described in the Protocol. All analyses will be exploratory. The performance of the statistical analysis for the protocol objectives and endpoints of the exploratory phase 2 study is contingent on the availability of the data source. Detailed information will be provided in the corresponding sections to follow.

### A. Primary

The protocol lists the following primary objective:

• To determine confirmed objective response with CMP-001 in combination with Nivolumab in subjects with refractory unresectable or metastatic melanoma.

### **B.** Secondary

The protocol lists the following secondary objective:

• To evaluate the safety and tolerability of CMP-001 administered by intratumoral (IT) injection in combination with Nivolumab in subjects with refractory unresectable or metastatic melanoma.

CONFIDENTIAL

### Statistical Analysis Plan

Regeneron Pharmaceuticals Inc. / Protocol: CMP-001-010 IQVIA Biotech (Confidential) Project # RZA44091

- To evaluate the efficacy of CMP-001 in combination with Nivolumab in subjects with refractory unresectable or metastatic melanoma.
- To assess the pharmacokinetic (PK) profile of CMP-001 in combination with Nivolumab in subjects with refractory unresectable or metastatic melanoma.
- To assess and describe the immunogenicity of CMP-001 in combination with Nivolumab in subjects with refractory unresectable or metastatic melanoma.

### C. Exploratory

The protocol (Section 2.1.3) lists the following exploratory objective:

- Evaluate the effect of CMP-001 in combination with Nivolumab on injected and non-injected target lesions in subjects with unresectable or metastatic melanoma.
- Evaluate the pharmacodynamic effects of CMP-001 administered in combination with Nivolumab.

## V. Study Endpoints

### A. Primary

The primary endpoint is the ORR, defined as the proportion of subjects with a confirmed objective response of CR or PR based on Response Evaluation Criteria in Solid Tumors version 1.1 (RECIST v1.1) as determined by Blinded Independent Central Review (BICR).

### **B.** Secondary

The protocol describes as secondary endpoints the following:

- AEs, serious adverse events (SAEs), and AEs leading to discontinuation or death, and severity of AEs as assessed by the National Cancer Institute (NCI) Common Terminology Criteria for Adverse Events version 5.0 (CTCAE v5.0)
- Duration of response (DOR), defined as the time from date of first documented response (CR or PR) to date of documented PD, based on RECIST v1.1 by BICR
- Treatment response in non-injected target lesions based on RECIST v1.1 by BICR
- Progression-free survival (PFS), defined as the time from date of first dose of study treatment to date of documented PD based on RECIST v1.1 by BICR or death, whichever occurs first

CONFIDENTIAL

## Statistical Analysis Plan

Regeneron Pharmaceuticals Inc. / Protocol: CMP-001-010 IQVIA Biotech (Confidential) Project # RZA44091

- Overall survival, defined as the time from date of first dose of study treatment to date of death
- ORR, DOR, and PFS based on RECIST v1.1 and immune objective response rate, immune duration of response (iDOR), and immune progression-free survival (iPFS) based on immunotherapy Response Evaluation Criteria in Solid Tumors (iRECIST) by Investigator assessment
- Blood concentrations of CMP-001 or its metabolites
- Development of anti-Qb antibodies

### C. Exploratory

In addition to the endpoints described above, the following endpoints will be evaluated:

- Response in injected and non-injected target lesions per intra-tumoral Response Evaluation Criteria in Solid Tumors (itRECIST) by Investigator assessment
- Baseline, and change from Baseline, in tumor or blood measurements of biomarkers related to TLR9, immune checkpoints, and potential markers of resistance or response to immunotherapy
- Change from Baseline in blood concentrations of CXCL10 (interferon gamma-induced protein 10) after treatment with CMP-001

# VI. General Analytical Considerations

Data analyses will be primarily descriptive and exploratory. Categorical variables will be summarized as the number and percentage of subjects within each category of the parameter (with a category for missing data, if applicable). Continuous variables will be presented as number (n), mean, median, standard deviation, and range (minimum and maximum). Discrete variables will be presented as frequencies or proportions.

Statistical analyses will be performed using SAS® software version 9.4 or higher.

#### A. Data Sources

Data are recorded on electronic case report forms (eCRFs). Central laboratory data will be provided via electronic data transfers. Protocol Section 11 and the study Data Management Plan provide additional details regarding data recording and handling.

### B. Definition of Baseline and Study Day

## Statistical Analysis Plan

Regeneron Pharmaceuticals Inc. / Protocol: CMP-001-010 IQVIA Biotech (Confidential) Project # RZA44091

Baseline is defined as the last non-missing observation prior to the first administration of study drugs (CMP-001 or Nivolumab). Study Day 1 will be designated as the first day a patient receives either study drug (i.e., Week 1 Day 1).

### C. Missing Data

Unless stated otherwise, missing data will not be replaced with imputed values. When relevant, sections below will address how missing data will be handled for the analyses.

### **Missing or Partial Death Dates**

A death date missing the month and day will be imputed as Jan 1st of the year or the date after the date of last contact, whichever comes last.

A death date missing the day will be imputed as the 1st of the month or the day after the date of last contact, whichever comes last.

### Missing Dates in Adverse Events/Concomitant Medications

Every effort will be made to avoid missing/partial dates in on-study data including AE and medication start and stop dates.

Start dates of AEs/Concomitant medications will be imputed as follows:

- Completely missing start date will not be imputed.
- Start date missing both the month and day will be imputed as:
  - The date of the first dose if the year of the start date is the same as the date of first dose.
  - Otherwise, Jan 1st of the year of the start date will be used.
- Start date missing the day will be imputed as:
  - The date of first dose if the year and month of the start date are the same as the date of first dose.
  - Otherwise, the 1st of the month of the start date will be used.

Stop dates of AEs/Concomitant Medications will be imputed as follows:

- Completely missing stop date will not be imputed.
- Stop date missing both the month and day will be imputed as Dec 31st of the year of stop date.
- Stop date missing the day will be imputed as the last date of the month of the stop date.

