# **EIQVIA**BIOTECH

### Statistical Analysis Plan

Regeneron Pharmaceuticals Inc. / Protocol: CMP-001-010 IQVIA Biotech (Confidential) Project # RZA44091

• After imputation, the imputed date will be compared against the date of death, if available. If the planned imputed date is later than the date of death, the date of death will be used as the imputed date instead. If there is no date of death in the EDC for a subject and the planned imputed date is later than the End-of-Treatment (the last drug received) date + 100 days, then the End-of-Treatment (the last drug received) date + 100 days will be used for the stop date.

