### **B.** Adverse Events

Adverse events should be recorded upon first occurrence and followed until resolution. A persistent AE is continuous and does not resolve between Q3W dosing visits and should be documented only once unless the grade becomes more severe. If the grade becomes more severe, the AE must be reported again with the new grade. Any recurrent AE should be reported as new AE each time the AE occurs. Worsening of an ongoing AE (i.e., an increase to higher grade) should be recorded as a new AE. Ongoing AEs that decrease in severity/grade should not be captured as new AEs.

Immune-mediated AEs can include events with an alternate etiology that were exacerbated by the induction of autoimmunity. In the EDC system, each AE is classified as immune-mediated or not by the Investigator.

Per protocol section 8.1.1, disease progression, and associated hospitalizations and deaths, are not considered an AE or SAE in this study.

Medical occurrences that begin before start of study treatment should be recorded on the Medical History/Current Medical Conditions section of the eCRF, not the AE section.

Adverse events starting more than 100 days after the last dose of study treatment should not be recorded on the AE eCRF unless they are considered to be related to study treatment.

Serious adverse events and AEs resulting in discontinuation will be followed until one of the following occurs:

- The event resolves
- The event stabilizes
- The event returns to a Baseline value if a Baseline value is available
- The event can be attributed to agents other than the study treatment or to factors unrelated to study conduct

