### Statistical Analysis Plan

Regeneron Pharmaceuticals Inc. / Protocol: CMP-001-010 IQVIA Biotech (Confidential) Project # RZA44091

• The Investigator and Medical Monitor agree that follow-up is no longer necessary

Adverse event (AE) data are available to the Sponsor from two sources: the eCRFs and the Serious Adverse Event (SAE) paper forms and corresponding SAE narratives. While reconciliation will be performed to ensure consistency between the two types of data, the production of data summaries and listings will be based on the data collected on the eCRF.

*Treatment-emergent adverse event (TEAE)* 

Pretreatment AEs are AEs that occur from the time of informed consent up to the first dose of study treatment (W1D1). A treatment-emergent adverse event (TEAE) is defined as an AE that started or worsened in severity on or after the date that study treatment was first administered (W1D1) until 100 days after the last dose of study treatment or a new cancer treatment is initiated, whichever occurs first.

Treatment-emergent adverse events will be coded using MedDRA (version 23.1 or later) and data will be summarized for the Safety Analysis Set. The number and percent of subjects reporting each TEAE will be summarized, as well as the number of TEAEs. A subject with 2 or more TEAEs within the same level of summarization (i.e., system organ class or preferred term) will be counted only once in that level using the most severe event or most related (for the relationship to study treatment tables).

AEs are graded using Common Terminology Criteria for Adverse Events (CTCAE) Version 5.0. AE summaries may include summaries for all AEs and by the maximum CTCAE grade for the item being summarized (i.e., SOC or PT). In these cases, the outputs will include a row for All Grades as well as rows for the 5 potential CTCAE grades: Grade 1 (Mild), Grade 2 (Moderate), Grade 3 (Severe), Grade 4 (Life threatening or disabling), or Grade 5 (Death).

If grade is missing for a TEAE, the event will be counted as grade 3=severe in the TEAE summary tables. If relationship is missing for a TEAE, the event will be counted as related in the TEAE summary tables.

An AE preferred term reported by a subject more than once will be represented in the most severe category or most related (for the relationship to study treatment tables).

A TEAE summary table will be generated including the following (N (%)):

- Subjects with one or more TEAEs
- Subjects with TEAEs of grade 3 or higher

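### Partial adverse event start dates are imputed to first dose without looking at the stop date, so an event that ended before dosing can be counted as treatment-emergent (minor)

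*SAP*

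**What the plan says.** SAP VI.C, under missing dates for AEs and concomitant medications, has three start-date rules.

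- No date at all: "Completely missing start date will not be imputed".
- Month and day missing: "The date of the first dose if the year of the start date is the same as the date of first dose"; when they differ, 1 January of the recorded year.
- Day missing: "The date of first dose if the year and month of the start date are the same as the date of first dose"; when they differ, day 1 of the recorded month.

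The only check after imputation stands at the end of the stop-date rules: "If the planned imputed date is later than the date of death, the date of death will be used as the imputed date instead". Where no death is recorded, the cap is last dose plus 100 days. No start date is compared with its own stop date.

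SAP IX.B defines a TEAE by timing: onset or worsening from the day of first dose until 100 days after the last dose or the start of a new cancer treatment, whichever is sooner. The same section recognises pretreatment AEs, which fall between consent and first dose. Protocol 7.6 and 8.3 require AEs to be captured on the eCRF from consent, and the Schedule of Assessments (Table 1) puts Screening at Day -30 to Day -1.

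**The concern.** Setting an uncertain start to the first-dose date is a reasonable conservative choice when the record cannot say whether the event came before or after dosing. It stops being reasonable when the stop date answers the question. An AE that stopped before first dose cannot have started on or after it, yet the rule as written moves its start to Day 1, past its own end, and the TEAE definition then counts it.

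The trial does collect AEs in the window where this can happen, and the window is short enough that onset and first dose often share a calendar month. Safety is a secondary objective and is reported mainly through TEAE summaries, so a pretreatment event can appear in those tables as one that arose on study treatment.

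Separately, an AE with no start date has no stated TEAE status. Two programmers could handle it differently and both claim to follow the SAP.

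**Working it through.** The plan states no figure on this point, so there is none to reproduce. The check applies the rules literally to test records.

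**Inputs.** Start-date rules and the post-imputation check: SAP VI.C. TEAE definition: SAP IX.B. Screening window: Protocol Table 1. Treated subjects: SAP II.C, 67 screened − 23 screen failures = 44. The dates below are hypothetical, with first dose on 20 Mar 2022.

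| Recorded start | Recorded stop | Start under SAP VI.C | Status under SAP IX.B | Start after stop? |
|---|---|---|---|---|
| 'Mar 2022' | 12 Mar 2022 | 20 Mar 2022 | TEAE | Yes, by 20 − 12 = 8 days |
| '2022' | 28 Feb 2022 | 20 Mar 2022 | TEAE | Yes |
| 'Feb 2022' | 28 Feb 2022 | 1 Feb 2022 | Pretreatment | No |
| 'Mar 2022' | ongoing | 20 Mar 2022 | TEAE | No |
| none | none | none | Not stated | – |

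Rows 1 and 2 are the error: the stop date shows the event was over before dosing. Row 3 is handled correctly. Row 4 is the case the rule was built for. The check against death or last dose plus 100 days cannot catch rows 1 and 2, because 20 Mar 2022 breaches neither limit.

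**Row 5.** With no date, the condition 'start on or after first dose' is not met, so a plain comparison leaves the event out. The worsening part of the definition does not rescue it, because "Worsening of an ongoing AE (i.e., an increase to higher grade) should be recorded as a new AE", with its own start date.

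**How often a pretreatment onset is exposed.** Assume onset is equally likely on each of the 30 days before first dose, and first dose is equally likely on any day of a 365-day year. There are 365 × 30 = 10,950 pairs of dates.

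- Same calendar month: a month of L days contributes L(L − 1)/2 pairs. Seven months of 31 days give 7 × 465 = 3,255, four of 30 days give 4 × 435 = 1,740, and February gives 378. Total 5,373; 5,373/10,950 = 49%.
- Same calendar year: only first doses on 1 to 30 January can have an onset in the previous year, giving 30 + 29 + … + 1 = 465 pairs. (10,950 − 465)/10,950 = 96%.

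So about half of Screening onsets would be exposed if the day were missing, and nearly all if month and day were missing. These are shares of onsets that the rule could reach. They do not say how many records have partial dates.

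**Size in the tables.** One reclassified subject moves an incidence by at most 1/44 = 2.3 percentage points, two by 4.5 and three by 6.8.

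**With the fix below.** Rows 1 and 2 become pretreatment, rows 3 and 4 do not change, and row 5 becomes a TEAE.

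**The case against.** The best case against is that the error needs several things at once: onset between consent and first dose, a partial start matching the first-dose month or year, a stop date that precedes dosing, and no correction by query. SAP VI.C promises every effort to avoid partial dates, and Protocol 8.3 requires onset date and time for every AE. SAP IX.B also directs medical occurrences from before treatment to medical history. Subjects count once per system organ class or preferred term, so a row changes only if the subject has no other TEAE there. All of this bears on frequency and stands. It does not change what the rule does when the case arises. Nor does the medical-history instruction empty the pool: Protocol 7.6 and 8.3 confine it to non-adverse events, and SAP IX.B keeps a pretreatment AE category.

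Three stronger readings are tempting, and the documents do not support them.

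- *An AE with no start date is excluded from every TEAE table.* The SAP leaves the date blank but nowhere says the event is excluded. Protocol 7.6 and 8.3 treat AEs reported on or after W1D1 as TEAEs, which would keep it. SAP I.B lets the SAP prevail where the two conflict, but on this point the SAP is silent. The overall SAE summary and the SAE listing are not titled as TEAE-only, and SAE forms are reconciled with the eCRF. The fair statement is that classification is not specified.
- *Leaving the date blank contradicts the SAP's worst-case handling of other missing items.* That handling begins "If grade is missing for a TEAE, the event will be counted as grade 3=severe in the TEAE summary tables". It applies to an event already classed as a TEAE and does not decide which events are TEAEs.
- *Pretreatment events are attributed to the drugs.* TEAE status is about timing. Relationship is assigned separately by the investigator, and Protocol Table 6 gives lack of a temporal association as a ground for 'Unrelated'. Such an event should reach the related-TEAE tables only if its relationship is also missing.

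**Conclusion.** The stop-date gap holds on the face of SAP VI.C: a stated rule produces a start after the stop and a TEAE that the record contradicts. The undated-AE point holds only as a missing statement of classification.

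Severity is minor. The number of affected records is unknown, because the documents give no count of partial or missing AE dates, and it is probably small. The limit of 2.3 percentage points per reclassified subject rests on the 44 treated subjects as denominator. The 49% and 96% shares rest on uniform onset over Screening and describe exposure to the rule only. The tables concerned are single-arm and descriptive, and the objective response rate and its confidence interval are unaffected. Where no stop date contradicts it, imputing to first dose remains the usual conservative choice and should stay.

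**What to change.** Make two additions to SAP VI.C.

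1. Impute a partial AE start to the first-dose date only if the stop date is missing or falls on or after first dose. Otherwise use the later of the consent date and the earliest date compatible with what was recorded (the 1st of the month, or 1 January if only the year is known), and never a date later than the stop date. The AE then stays pretreatment. A partial stop date can be tested after its own imputation: VI.C already takes the last day of the recorded month or year, so a stop that still precedes first dose settles the matter.
2. An AE with a completely missing start date counts as a TEAE unless its stop date is before first dose, or other recorded information places its onset outside the TEAE window in SAP IX.B, including the limit of 100 days after last dose or new cancer treatment.

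The cost is two sentences and a small change to the derivation program, with no new data. The first addition can only lower TEAE counts. The second may raise them slightly compared with a literal date comparison. A listing of AE records with a missing start, or with an imputed start after the stop, would show before the final tables whether either case occurs.

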# **EIQVIA**BIOTECH

### Statistical Analysis Plan

Regeneron Pharmaceuticals Inc. / Protocol: CMP-001-010 IQVIA Biotech (Confidential) Project # RZA44091

• After imputation, the imputed date will be compared against the date of death, if available. If the planned imputed date is later than the date of death, the date of death will be used as the imputed date instead. If there is no date of death in the EDC for a subject and the planned imputed date is later than the End-of-Treatment (the last drug received) date + 100 days, then the End-of-Treatment (the last drug received) date + 100 days will be used for the stop date.

### **Missing Dates in Prior Medications**

Start or Stop dates of Prior Medications will be imputed as follows:

- Completely missing start or stop date will not be imputed.
- Start or stop date with missing both the month and day will not be imputed.
- Start date missing the day will be imputed as the 1st of the month of the start date.
- Stop date missing the day will be imputed as the last date of the month of the stop date or the study first dose date, whichever comes earlier.

### **D.** Multiple Study Centers

No adjustment for study center is planned.

### E. Covariate Adjustment in Primary Analysis

No covariate adjustments are planned.

### F. Sample Size Reassessment

Not applicable.

### G. Ad-hoc Analysis

There will be an ad-hoc analysis planned with the trigger event being two disease assessments after the enrollment of the last subject. The ad-hoc analysis of the endpoints will follow the efficacy analysis methods described in Section VIII below as well as the safety analysis methods detailed in Section IX below for the exploratory Phase 2 study.

The following subject information, efficacy-related and safety related data displays will be produced for the purpose of the ad-hoc analysis. Unless stated

